8.1.4 Month 1 Visit

Subjects will be seen at month 1 for clinical assessment (interval history and targeted exam) and review of drug adherence. Blood will be drawn. They will then take their daily ART and study drug and will remain in the MCRU for additional blood draws at 1, 2, 3, 4, 6, 8, and 12 hours after drug administration in order to intensively study the pharmacokinetics of ARTs and losartan. They will then return to the MCRU the following morning for one additional blood draw at 24 hours after drug administration.

8.1.5 Months 3, 6, 9, 15, 18, 21 and 27 Visits

Subjects will be seen for clinical assessment (interval history and targeted exam), review of drug adherence, refill of study drug, and blood draw for CBC, CMP, CD4, VL, plasma, serum and PBMCs.

8.1.6 Month 12 Visit

Subjects will be seen at month 12 for clinical assessment (interval history and targeted exam), review of drug adherence, refill of study drug, and blood draw for CBC, CMP, CD4, VL, plasma, serum and PBMCs. Subjects in the two-photon microscopy sub-study will also have an additional 90cc of blood drawn. Subjects will then undergo repeat inguinal LN biopsy and colonoscopy with rectal and ileal biopsies. They will remain in the MCRU for 4 hours after procedures for clinical monitoring.

8.1.7 Month 23 Visit

Subjects will be seen for clinical assessment (interval history and targeted exam), review of drug adherence, refill of study drug, and blood draw for CBC, CMP, CD4, VL, plasma, serum and PBMCs. In addition, the first dose of Gardasil (human papillomavirus recombinant vaccine) will be administered. Subjects will remain in the MCRU for 30 minutes after administration for monitoring.

8.1.8 Month 25 visit

Subjects will return for clinical assessment (interval history and targeted exam), review of drug adherence, refill of study drug and blood draw for plasma, serum and PBMCs. The second dose of Gardasil will then be administered. Subjects will remain in the MCRU for 30 minutes after administration for monitoring.

8.1.9 Month 29.5 Visit

Subjects will be seen for clinical assessment (interval history and targeted exam), review of drug adherence and blood draw for CBC, CMP, CD4, VL, plasma, serum and PBMCs. In addition, the third and final dose of Gardasil will be administered. Subjects will remain in the MCRU for 30 minutes after administration for monitoring.

8.1.10 Month 30 Visit (Final Study Visit)

Subjects will be seen at the end of month 30 for the final scheduled study visit. Clinical assessment (interval history and targeted exam) and review of drug adherence will be performed and any remaining study drug will be collected by the designated study staff. Blood will be drawn for CMP, CBC, HIV VL, CD4 T cell count, serum, plasma, and PBMCs. Subjects in the two-photon microscopy sub-study will also have an additional 90cc of blood drawn. Subjects will undergo final biopsy procedures (ileal, rectal, and lymph node). They will remain in the MCRU for 4 hours after procedures for clinical monitoring. They will complete the off-study form prior to discharge from the MRCU. Subjects will be instructed to report any subsequent event(s) within 3 months of study completion that the subject, or the subject's personal physician, believes might reasonably be related to participation in this study.

8.1.11 Early Termination Visit

Participants may withdraw voluntarily from the study at any time. If a subject opts to discontinue, attempts will be made to schedule and conduct an early termination visit for medical assessment and return of any unused study drug for proper disposal. If a subject withdraws after an adverse event (AE), they will be followed until resolution of the issue or until their condition is stable.

8.1.12 Pregnancy Visit

In the event that a study subject becomes pregnant, termination, reporting, and follow-up procedures outlined in Section 9.9 will be followed.

8.1.13 Unscheduled Visits

Additional visits will be scheduled as needed to follow up AEs, evaluate biopsy sites, address subject concerns, etc.

8.2 Schedule of Events for HIV Infected Subjects

Table 1. Protocol summary for HIV infected subjects:

	Screen	Day 0	Day 14	Month 1	Months 3, 6, 9, 15, 18, 21, 27	Month 12	Month 23	Month 25	Month 29.5	Month 30
Medical history	X	X								
Interval medical history			X	X	X	X	X	X	X	X
Physical Exam ¹	X	X	X	X	X	X	X	X	X	X
Adherence assessment and counseling		X	X	X	X	X	X	X	X	X
Pregnancy test ²	X	X		X	X	X		X	X	
HCV Ab	X									
CMP	X	X	X	X	X	X	X		X	X
CBC w diff	X	X	X	X	X	X	X		X	X
CD4 count	X	X		X	X	X	X		X	X
HIV viral load	X	X		X	X	X	X		X	X
Serum ³		X		X	X	X	X	X	X	X
Plasma /PBMCs ⁴		X		X	X	X	X	X	X	X
Additional PBMCs ⁵		X				X				X
Biopsies ⁶		X				X				X
HPV vaccine ⁷							X	X	X	
PK assessment				X ⁸	X ⁹	X ⁹		X ⁹		X ¹⁰

1. At screening, a full physical exam will be performed (described above). At subsequent visits, a targeted exam will be performed.
2. Women of childbearing age must have a negative pregnancy test prior to enrollment. Pregnancy testing will also occur roughly every 3 months during follow up and additionally if the subject or investigator suspects pregnancy.
3. Serum will be used to determine levels of IL-7 and TGF-beta.
4. Plasma will be used to determine levels of cytokines and markers of inflammation. PBMCs will be used in flow cytometry and intracellular cytokine staining.
5. Additional blood will be obtained from subjects enrolled in the two-photon microscopy sub-study.
6. Inguinal LN biopsy and colonoscopy with sampling of ileal and rectal tissues.
7. Human papillomavirus quadrivalent vaccine (Gardasil) will be administered at 3 time points per recommended vaccine schedule and immune response will be assessed at month 30.
8. Intensive 24-hour PK assessment will be performed at month 1 visit.
9. Plasma and intracellular PBMC concentration of losartan and ARVs will be determined approximately every quarter.
10. Plasma and intracellular PBMC concentration of losartan and ARVs PLUS concentrations in LN and GALT will be determined at month 30.

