2.2 Study Hypothesis and Rationale

Our hypothesis is that treatment of HIV infected subjects with losartan, which has specific anti-inflammatory and anti-fibrotic actions will: 1) reverse existing fibrosis, 2) restore LN architecture, 3) increase the number and improve the function of peripheral and lymphatic CD4 T cells, 4) decrease levels of IA, 5) decrease HIV reservoirs, and 5) be safe and well tolerated. To address this hypothesis, we will enroll HIV infected subjects and randomize them 1:1 to losartan vs placebo, then serially sample blood and LT. In similar longitudinal tissue biopsy protocols our drop-out rate has ranged from 20-25%. Therefore, we plan to enroll 63 HIV infected subjects in order to have 50 complete the protocol. All HIV infected subjects randomized to losartan will initiate therapy at a dose of 50 mg per os (po) daily and increase the dose to 100 mg po daily if they have no side effects or laboratory abnormalities after 14 days. This is standard losartan dosing for the treatment of hypertension and stroke reduction. This dosing protocol was also used and was well tolerated by non-hypertensive subjects in a large clinical trial assessing the anti-fibrotic effect of losartan in patients with Marfan syndrome [48]. Given risk of teratogenicity with losartan, all female subjects of reproductive age who are enrolled in the protocol will be required to use a reliable and effective method of contraception for the duration of the study. Lymphatic tissue biopsies for primary endpoint analysis will be obtained at baseline and 12 and 30 months after initiation of losartan or placebo. We are following subjects for 30 months because we felt that a long period of follow up may be required to discern a significant difference in the treatment groups given the persistence of LT fibrosis in subjects treated with ART alone (unpublished data). HIV infected subjects will also be administered the human papillomavirus (HPV) quadrivalent vaccine (Gardasil) per the manufacturer's recommended dosing schedule to assess immune response (a secondary endpoint). Gardasil vaccine is FDA-approved for use in men and women ages 9 to 26 to prevent the complications related to infection with HPV types 6, 11, 16 and 18. Although not approved for adults >26 years of age, the vaccine has been well-studied in older populations and has been found to be safe and well-tolerated [49-51]. It is expected that many study subjects will have been exposed to 1 or more of the HPV serotypes included in the vaccine; however, based on epidemiologic data, it is not expected that subjects will have been exposed to all 4 serotypes [52-54]. Therefore, this vaccine can be used to assess both neo and recall immune responses. Vaccination will be initiated at the end of the study to maximize time on study drug prior to vaccination and to ensure that tissues are collected at time of maximal immune response.

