4.2.2 Secondary Endpoints

There are 4 secondary endpoints:

1. We will assess the impact of losartan on immune reconstitution and T-cell function by measuring:

- ⇒ Frequency of CD4+ T cells, TUNEL+CD3+CD8+ T cells and cells expressing TGF-beta and lymphotxin-beta in LT using IHC.
- ⇒ Serum levels of IL-7 and TGF-beta using ELISA.
- ⇒ The immune response to HPV vaccination using flow cytometry to identify cells stimulated by specific HPV peptides.

2. We will determine the impact of losartan on immune activation in HIV infected, treated individuals by determining:

- ⇒ Frequency of activated T-cell populations (specifically CD3+CD4+CD38+, CD3+,CD8+CD38+, CD4+Ki67+ and CD8+Ki67+ T cells) in LT using immunofluorescence staining.
- ⇒ Percentage of activated T cells, macrophages and dendritic cells in PBMCs and LT using flow cytometry.
- ⇒ Intracellular levels of the inflammatory cytokines IL-17, IFNg, IL-2, TNF, IL-10, and GM-CSF in PBMCs and LT using cytokine staining.
- ⇒ Plasma levels of additional inflammatory markers including LPS, sCD14, I-FABP, IL-1b, IL-1RA, IL-6, TNF, amyloid A, CRP, and D-dimer using limulus assay (sCD14) and ELISA (all others).

3. We will assess the potential for losartan to reduce the size of the viral reservoir by determining the frequency of HIV RNA+ and DNA+ cells in LN and GALT using both radiolabeled in situ hybridization (ISH) and RNAscope™ in situ technology.

4. To ensure that losartan is safe and well tolerated when used with ART, we will:

- ⇒ Perform an intensive pharmacokinetics experiment in all HIV infected subjects at month 1 of the study (when losartan is at steady state).
- ⇒ Measure levels of ARTs and losartan in plasma and PBMCs quarterly over the 30-month study period.
- ⇒ Measure intracellular levels of losartan and ARTs in LT at month 30.

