5. Prior diagnosis of a chronic inflammatory disease with serologic or clinical evidence as diagnosed by a primary care physician or specialist. Examples of these include, but are not limited to, systemic lupus erythematosus, rheumatoid arthritis, scleroderma, Sjogren's syndrome, mixed connective tissue disease, psoriasis, polymyositis, dermatomyositis, vasculitis, sarcoidosis, Wegener's granulomatosis, giant cell arteritis, polyarteritis nodosa, gastrointestinal pemphigoid, eosinophilic colitis, Crohn's disease, ulcerative colitis, autoimmune hepatitis.
6. Prior diagnosis of a connective tissue disease with genetic, serologic or clinical evidence as diagnosed by a primary care physician or specialist. (Marfan's syndrome, Ehlers-Danlos syndrome).
7. Screening systolic blood pressure < 110.
8. Estimated Glomerular Filtration Rate (eGFR) of < 30ml/min/1.73 m² within 60 days of study initiation or history of advanced renal disease.
9. AST and/or ALT > 3 times the upper limit of normal within 60 days of study enrollment.
10. Potassium > 5.0 within 60 days of study enrollment.
11. Pregnancy.
12. In women of childbearing age, unwillingness to use birth control for the duration of the study.
13. Breast feeding.
14. Prior vaccination with an HPV vaccine, including Cervarix (GlaxoSmithKline) or Gardasil (Merck).
15. History of hypersensitivity or severe allergic reactions to yeast.
16. At the principle investigator's discretion if not a suitable surgical candidate.
17. Currently undergoing treatment for hepatitis C or treatment completed within the last 3 months
18. History of ≥ 3 previous inguinal lymph node biopsies

HIV-uninfected:

a. Inclusion Criteria

Participants must meet all of the following inclusion criteria to participate in this study:

1. HIV uninfected.
2. ≥ 18 years of age.
3. No contraindication to proposed study procedures.

b. Exclusion Criteria

Participants meeting any of the following exclusion criteria at baseline will be excluded from study participation:

1. Use of any immunomodulator within the 12 months prior to study enrollment (as defined above).
2. Current use of an ARB or ACEi.
3. Prior diagnosis of a chronic inflammatory disease with serologic or clinical evidence (as defined above).
4. Prior diagnosis of a connective tissue disease with genetic, serologic or clinical evidence as diagnosed by a primary care physician or specialist. (Marfan's syndrome, Ehlers-Danlos syndrome).

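### HPV response is read only at month 30, so responses cannot be classed as new or recall and change from pre-vaccination cannot be estimated; pre-dose cells already drawn could supply both.

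*Combined protocol and SAP*

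**What the plan says.** - **Aim.** Section 2.2 expects that "many study subjects will have been exposed to 1 or more of the HPV serotypes included in the vaccine", though not to all four, and concludes that "this vaccine can be used to assess both neo and recall immune responses". It gives no exposure percentage.
- **Endpoint.** Section 4.2.2, under secondary endpoint 1 (immune reconstitution and T-cell function), lists "The immune response to HPV vaccination using flow cytometry to identify cells stimulated by specific HPV peptides". It states no time point, pre-dose value, result by type or definition of naive.
- **Read-out.** Table 1, footnote 7, after describing the three vaccinations, says that "immune response will be assessed at month 30".
- **Entry control.** Section 5.2 excludes "Prior vaccination with an HPV vaccine". Natural exposure is neither excluded nor measured. Footnote 3 of Table 1 lists serum only for IL-7 and TGF-beta, so no HPV serology is named.
- **Samples.** Table 1 shows PBMCs drawn at day 0 and at later visits. Under Section 8.1.2 the day 0 blood precedes randomisation. Section 8.1.7 lists "blood draw for CBC, CMP, CD4, VL, plasma, serum and PBMCs. In addition, the first dose of Gardasil" for month 23. Footnote 4 gives PBMCs a general flow-cytometry and cytokine-staining use. Handling is left to a Specimen Management Plan that is not among the documents.
- **Analysis.** Sections 11.1 and 11.5 plan mixed models for longitudinal outcomes; Section 11.1 specifies arm, time and arm-by-time terms.

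**The concern.** A new response is one in a person not primed to that HPV type before dose 1; a recall response is one in a person who was. Telling them apart needs each participant's pre-vaccine status for each type. The only reading named comes after all three doses. A positive result for a type at month 30 could be newly induced, boosted, or present and unchanged throughout. Excluding earlier vaccination does not settle this, because the plan itself expects natural exposure to be common.

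The same gap affects the analysis. The general model tests whether the arms change at different rates, and an outcome measured once has no rate of change. Followed as written, the plan delivers a cross-sectional arm comparison for this outcome. It does not deliver the new/recall reading that Section 2.2 offers as a reason for using this vaccine.

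**Working it through.** **1. The plan's own power figures.** Section 11.2 gives power only for collagen: SD 0.81 (log scale), 25 per arm. I assume two-sided alpha of 0.05, since Section 11.5 gives no number. With power = Φ(δ / (0.81·√(2/25)) − 1.96), differences of 0.5, 0.6, 0.7 and 0.8 give 0.588, 0.745, 0.863 and 0.937, against the stated 0.59, 0.75, 0.86 and 0.94. The table reproduces but says nothing about HPV response, for which the documents give no SD, effect or exposure rate.

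**2. Can the planned model be fitted?** This step needs no assumption. The columns are intercept, arm, time and arm × time.
- Month 30 only: time = 30 × intercept and arm × time = 30 × arm. The rank is 2 of 4, so neither the time effect nor the interaction can be estimated.
- One pre-dose time added (day 0 or month 23): the rank is 4 of 4.

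**3. Precision forgone.** Adjusting month 30 for a pre-dose value with correlation ρ multiplies the variance by 1 − ρ². The values of ρ and the standardised effect of 0.8 are assumptions; power uses residual SD √(1 − ρ²).

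| ρ (assumed) | Variance cut | 25 per arm acts like | Power at effect 0.8 |
|---|---|---|---|
| 0 (no adjustment) | 0% | 25 | 0.81 |
| 0.3 | 9% | 25/0.91 = 27.5 | 0.84 |
| 0.5 | 25% | 25/0.75 = 33.3 | 0.90 |
| 0.7 | 49% | 25/0.51 = 49.0 | 0.98 |

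**4. How much a new/recall split could show.** Suppose 20%, 40% or 60% are already exposed to a given type.
- Naive participants per arm: 25 × (1 − share) = 20, 15 or 10. Power at effect 0.8 is 0.72, 0.59 or 0.43.
- Exposed participants per arm: 5, 10 or 15. Power is 0.24, 0.43 or 0.59.

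Even with a baseline, the split is descriptive rather than confirmatory.

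**5. Limits of a cell assay as an exposure test.** Assume 40% are exposed and specificity is 0.95. The share of those called naive who are in fact exposed is 0.4(1 − sensitivity) / [0.4(1 − sensitivity) + 0.6 × 0.95]. Sensitivities of 0.5, 0.7 and 0.9 give 26%, 17% and 7%.

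**6. Which pre-dose sample?** Day 0 blood is drawn before randomisation, so treatment cannot have altered it. Month 23 follows about 23 months of losartan or placebo, and Section 2.2 hypothesises that losartan improves CD4 T-cell function. HPV-peptide reactivity at month 23 may therefore already carry a treatment effect. Adjusting for it, or forming subgroups from it, could remove part of the effect under test.

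**The case against.** **A pre-dose run may already be intended.** Section 11.1 treats all aims as longitudinal, PBMCs are drawn at each vaccine visit, flow cytometry is their listed use, and the HPV endpoint is a flow assay. Footnote 7 does not rule out an earlier comparator, and details may sit in files not supplied. This is fair, but footnote 4 is generic and nothing assigns an HPV test to any pre-dose sample. If one is intended, the protocol needs to say so.

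**The endpoint does not mention new or recall.** That language is a rationale statement in Section 2.2. The endpoint concerns losartan's effect on T-cell function, and a randomised, blinded comparison at month 30 addresses it. This stands. A reader might infer that the vaccine endpoint cannot answer its question at all; the documents do not support that.

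**Chance imbalance in prior exposure.** A reader might infer that it biases the arm comparison. With assumed exposure of 20% or 40% and 25 per arm, the SD of the arm difference is √(2 × 0.2 × 0.8/25) = 11.3 or √(2 × 0.4 × 0.6/25) = 13.9 percentage points. That is ordinary sampling variation, already reflected in the standard error. It costs precision and is not bias.

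**Ready-made cells.** A reader might infer that stored pre-dose cells would settle everything. The documents show that cells are drawn, not that they are stored. PBMCs also serve other flow assays, cytokine staining and drug levels. Section 8.1.7 lists the month-23 blood ahead of the vaccine but does not state the order outright. Blood also gives no pre-vaccine baseline for the draining-node response described in Section 7.1.5; the only pre-vaccine nodes are from day 0 and month 12. These limits stand and shape the fix.

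**Conclusion.** The point holds within limits. Month 30 is the only HPV read-out named, so the plan as written cannot class responses as new or recall and cannot estimate change from pre-vaccination. The arm-by-time model cannot be fitted to this outcome (rank 2 of 4). These conclusions rest on the plan's text and need no assumed figures.

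The randomised comparison at month 30 remains valid. Its loss is one of precision: a 9% to 49% variance reduction forgone for assumed correlations of 0.3 to 0.7. The benefit from a day 0 covariate may lie toward the low end, since that sample precedes the final reading by 30 months.

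The point concerns one component of one secondary endpoint. It merits correction because pre-dose blood is already drawn, not because the trial's main conclusions are at risk.

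**What to change.** Amend footnote 7 of Table 1 and the HPV item in Section 4.2.2 to state that:

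1. PBMCs from day 0 and from month 23, the latter drawn before the injection, are kept and run with the month-30 sample in the same HPV-peptide flow assay, with results by HPV type.
2. Naive or exposed status for each type is set from the day 0 result, using a cut-off fixed before unblinding.
3. The month-30 arm comparison is adjusted for the day 0 value. New and recall results by type are reported as descriptive, given the subgroup sizes.
4. Month 23 is used only to describe change over the vaccination course, because it is post-randomisation. It is neither a covariate in the arm comparison nor a basis for subgroups.

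**Cost.** Two further assay runs per participant (day 0 and month 23) and the PBMC aliquots they consume; no new visit, draw or procedure. The sponsor must first confirm that viable aliquots exist or can be reserved.

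**Limits to state alongside.** A cell assay may miss some past exposure, a day 0 class does not capture exposure acquired before month 23, and the node response still lacks a baseline immediately before vaccination.

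**If no viable pre-dose cells are available,** withdraw the new/recall statement in Section 2.2 and describe the HPV outcome as a single comparison of the arms at month 30.

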8.3 Schedule for Control - HIV Uninfected Subjects (n=5)

8.3.1 Screening

At this visit, consents will be reviewed in detail and the subject will have the opportunity to ask any questions they may have. The designated study staff or physician will interview the participant and a physical exam will be performed. Blood will be obtained for HIV antibody, liver function tests, electrolyte panel including creatinine, and CBC. Screening for hepatitis C will also be performed. Women of childbearing age will have a urine pregnancy test. Once lab results are available (within 3 days), they will be reviewed by designated study staff to ensure that laboratory inclusion/exclusion criteria are met. If the subject has met all entry criteria, they will be contacted by the designated study staff. The study protocol will again be reviewed and if the subject is still interested in enrolling, they will be scheduled for the study visit. Subjects who have not met the criteria will also be contacted by the designated study staff and told that they do not qualify to participate in the study.

8.3.2 Study Visit

Designated study staff will review medical history with the participant and perform a targeted physical exam. Blood will then be drawn for CD4, plasma, serum and PBMCs. Inguinal LN biopsy will be performed. The subject will remain in the MCRU for 4 hours after procedures for monitoring. They will complete the off-study form prior to discharge from the MRCU. Subjects will be instructed to report any subsequent event(s) within 3 months of study completion that the subject, or the subject's personal physician, believes might reasonably be related to participation in this study.

